First, the scientific rationale rests with the availability of a program to standardize lipid measurements of all of these laboratories. The Centers for Disease Control Lipid Standardization Program has provided this service for NHLBI-supported laboratories for decades. Two of the laboratories (MIBH and UM) have been long term participants in this program. During DELTA Diet Protocol I, several challenges sent from CDC to all four field center laboratories demonstrated that the accuracy and precision of these laboratories is comparable and the data that would be generated from them would have no greater variance than that generated by a single lab. These results are summarized in Tables 1 and 2. The first challenge to five centers is shown with labs in lower case type. The second challenge (to MINN and MIBH) is shown in capital letters. All data are summarized in a single statistical analysis.

Most field center budgets have, as part of the personnel budget, support persons to do the sample collection, aliquoting, and storage. These personnel are needed regardless of where the analyses take place. The preservation of some laboratory charges at the field center allows the support for these essential personnel.

The inclusion of glucose and uric acid at the local field laboratory is based on the ease and cost effectiveness of including them in the same analytical run on the same multichannel analyzer as is used to perform the lipid profile and the recognition that standard materials are available to calibrate for these analytes and that national proficiency testing programs (such as that operated by the College of American Pathologists) demonstrate that the various multichannel analyzers used by the field laboratories are adequately accurate and precise to assure statistical validity in endpoint analysis.

2. Central laboratories for other endpoint data

Insulin, the apolipoproteins (apo A-1, B, Lp (a)), apo-E genotypes, and coagulation factors (fibrinogen, factor VII, and PAI-1, beta-thromboglobulin) currently have no standardization programs available to provide laboratory standards. C-reactive protein and microalbuminuria require special standardization at low levels, not part of usual clinical measurement of the these analytes. Tests such as LDL size, VLDL-cholesterol, HDL-subfractions, retinyl esters, platelets by flow cytometry, involve multiple steps in preparation and analysis of samples and are best carried out at a single site to assure uniformity in handling and analysis.

Thus, the optimal way to control precision and accuracy is to use a central laboratory with recognized experience and methods for each of these tests. These laboratories were selected by the Steering Committee based on expertise and interest in performing the tests.

V. Quality Control

The DELTA Study requires this considerable effort to standardize blood collection, processing, and storage, since it involves four U.S. field centers and at least five laboratories. This protocol is necessitated by the importance of all sample collection procedures being feasible and of high quality in order to meet all the investigators' needs. The protocols for sample collection, processing, handling, storage and shipping will be similar to that for DELTA Diet Protocol I.

To assure validity of the results in this study requires rigid adherence to collection, labeling, and shipping protocols:

Training. To ensure that protocols are well understood, a training session will be held to provide training and experience before the beginning of the project. A training session will be held at each Field Center and will be coordinated by the laboratory point person for that center. (The laboratory point person is an individual who participated in a special training program before the initiation of DELTA Protocol 1 and who was designated by the Field Center as the person who would assume responsibility for training and certifying new personnel.) Since many of the endpoints are the same as for diet Protocol 1 (lipid profiles, apolipoproteins, ApoE genotyping, fibrinogen, PAI-1 and Factor VII) the details of blood drawing and processing will be the same as for Protocol 1. Several new test for Protocol 2 will require special sample handling (platelets, betathromboglobulin, microalbuminuria). A video tape will be prepared by the University of Vermont demonstrating the phlebotomy and sample processing for the testing for DELTA Protocol 2 with special emphasis on the new techniques that will be needed.

Written Protocols. Detailed instructions will be provided for each step in the collection and processing of samples. These will be compiled in the Manual of Procedures and will provide the basis for the on-site training programs.

Documentation. Forms will be provided to document each step of the blood (or urine) collection process with space for field center staff to describe any variation from the prescribed protocol. Additional forms will be used to validate the processing of the samples, including time from collection to freezing, maintenance of desired temperature during processing, and identification of any deviation from protocol during the processing and aliquoting.

Labeling. Processing and archiving includes detailed descriptions of how to set up tubes, makes provisions for assuring that correct identification labels are placed on each sample and provides a system for archiving that is redundant in identification (by label, by color code and by position in the freezer storage box).

Shipping. Shipping protocols are specific in detailing amount of dry ice and quantity of samples per box. Shipping protocols require double checking by shipper and by receiver that the packing list is correct, that the labels are attached and that there is no evidence that the sample has thawed either in storage or in transit. Sender must inform the recipient on the day of shipment that samples have been sent. If samples are not received the next day, the sender is informed and the shipping agent (Federal Express) is notified to search for the shipment.

Analysis. Specific recommendations are made for analysis of samples from each subject to assure completeness in results generated and assuring best possible analytical precision in analysis. Samples will be coded such that all samples from a single subject can be identified and grouped into three sets, from each of the three diet phases. These will be analyzed for each analyte on a single run for the analyte.

Quality control. All analytical runs will include appropriate quality control samples to assure the validity of the run. Quality control samples will be analyzed at specific intervals with each run as specified by the manual of operation for the laboratory performing the analysis. If the quality control materials do not meet the criteria set by the laboratory's manual of operation, the run must be rejected and repeated in total.

Adherence to these protocols, including periodic reviews and retraining, is the responsibility of each field center.

VI. Standards of Laboratory Practice

Laboratory work for DELTA will adhere to a designated standard of laboratory practice that assures that results are generated in a standard fashion and that original data are retained and available for review for a fixed period, should that be necessary.

The Laboratory Subcommittee is in the process of developing a document to serve as a Standard of Laboratory Practice. This document will be in the form of a checklist for evaluation of all the field and central laboratories that participate in DELTA. This standard of laboratory practice will detail the ways that data are generated for future review and will identify the extent to which the operator and supervisor will be expected to review and document their review of calibration, quality control, and subject results for each analyte, This will be similar to the "Good Laboratory Practice" standard that is usually applied to laboratories performing contract work for government and industry, but will be adapted to apply to the special situation of research work performed in research settings.

Table 1 Laboratory Tests	by Priority of Assay				
TEST	SITE	TEST SCHEDULE			
	tests/diet phase	timing (wee	ek #)		
Obligatory Tests for					
Study Hypotheses					
Lipid Profile	Local Lab	3	5,6,7		
Glucose	Local Lab	3	5,6,7		
Insulin	MIB	3	5,6,7		
Factor VII	Vermont	3	5,6,7		
Fibrinogen	Vermont	3	5,6,7		
PAI-1	Vermont	3	5,6,7		
Tests Which Should Be Perfo	ormed				
To Support Hypothesis Testin	ıg				
Apo E	MIB		once per subject		
LDL Size	Pennington	3	5,6,7		
Beta Thromboglobulin	Vermont	3	5,6,7		
VLDL-C	MIB	2	6,7		
HDL Subfractions	Columbia	2	6,7		
Apo A-1 and Apo B-100	Columbia	3	5,6,7		

.

Tests	Which Allow	Subhypotheses
To Be	e Tested	

Post-prandial standard fat load	i *		
Triglyceride	Local Lab	2	7; @ 4 h & 8 h
Glucose	Local Lab	2	7; @ 4 h & 8 h
Insulin	MIB	2	7; @ 4 h & 8 h
Retinyl ester	Columbia	2	7; @ 4 h & 8 h
Post-prandial post meal testin	g* .		
Triglyceride	Local Lab	2	6; before lunch & dinner
Glucose	Local Lab	2	6; before lunch & dinner
Insulin	MIB	2	6; before lunch & dinner
Lipoprotein (a)	MIB	3	5,6,7
Tests Which Allow New Mech to Be Explained	hanisms		
Platelets by Flow Cytometry	Vermont	1	6 or 7
C-reactive Protein	Vermont	3	5,6,7
Uric Acid	Local Lab	3	5,6,7
Microalbuminuria	MIB	3	5,6,7

*will be carried out on same day that fasting samples are collected for other testing for that week. In that way the fasting results for triglyceride, glucose and insulin will be available for comparison.

Once per	week to give 3 sets per diet period		Once per subject	Once per	r diet period
	package similar to Protocol 1 ubes of blood (41 mL)	Urine first AM	Buffy Coat	Platelets Special Prep	Postprandial (collection for two timed samples)
Serum 2x10 mL	Citrated Diatube EDTA plasma plasma plasma 2x4.5 mL 5 mL 7 mL	Urine		Platelets special	Serum 2 x 10 mL
14 vials	3 vials (4°) 3 vials 4 vials 3 vials (r.t.)	2 tubes	4 buffys	4 tubes	2 vial (foil wrapped) 3 vials

Disposition	of	vials	and	tubes
-------------	----	-------	-----	-------

:	serum	citra plas 4°	ma	Diatube plasma	EDTA plasma	buffy	urine	platelets	postprandial
Lipid profile, glucose	2								
HDL-subfractions	2								
VLDL-chol	1								
Uric acid	1								
Apo A/B, $Lp(a)$	1								
Insulin	1					_			
Apo E						1			
Fibrinogen		1							
PAI-1		1							
Factor VII			1						
Beta thromboglobulin*				1					
CRP	1							2	
Platelets							1	2	
Microalbuminuria					2		1		
LDL size					2				
Postprandial									1
Lipid profile, glucose Insulin									1
									1
Retinyl palmitate									-
Archive	5	1	2	2	2	3	1	2	2

.

۰.

* β -thromboglobulin requires filtering of the sample prior to freezing.

•

Table 3: DELTA PROJECT -- TOTAL CHOLESTEROL PRECISION

within laboratory

CV-total

	pool 61		pool 66		pool 67		pool 71	
lab	mean	cv	mean	cv	mean	CV	mean	cv
colu			183	0.7	220	0.9	274	0.6
loui			178	0.9	216	1.0	263	0.7
mibh			182	1.3	219	1.2	274	1.2
minn			175	1.9	210	1.6	257	1.6
stan			184	0.4	220	0.6	272	0.5
MI82	207	1.4	181	1.0			273	0.8
MIN2	206	1.3	182	1.5			267	1.4
MEAN >	207	1	181	1.1	216	0.8	269	1.0

DELTA PROJECT -- HDL PRECISION

within laboratory

CV-total

	pool 36		pool 81		pool 88	
lab	mean	cv	mean	cv	mean	CV
colu	60	0.9	40	1.3	27	1.9
loui	56	1.9	38	1.4	27	2.1
mibh	60	2.0	40	2.0	28	2.2
stan	60	1.1	41	0.8	29	0.9
MIB2	61	1.4	41	1.4	28	1.7
MIN2	58	2.2	40	2.3	28	1.4
MEAN>	58	1.6	39	1.5	27	1.6

				Table 4:	DELT	A PROJECT	TOTAL CHO	LESTE	ROL PRECI	SION				
	POOL 61		%	POOL 66		%	POOL 67		%	POOL 71		%	MEA	
	VARIANCE	cv	TOTAL	VARIANCE	CV	TOTAL	VARIANCE	CV	TOTAL	VARIANCE	CV	TOT	N	N
												AL	CV	% TOT AL
TOTAL	10.2	1.5	100	12.9	2.0	100	22.2	2.2	100	48.7	3.2	100	1.9	100
LAB	0.0	0.0	0	8.1	1.6	62	15.3	1.8	69	39.8	2.9	82	1.1	43.7
RUN	8.2	1.4	81	2.4	0.9	18	4.5	1.0	20	4.0	0.9	8	1.1	39.7
REPS.	2.0	0.7	19	2.5	0.9	20	2.5	0.7	11	4.8	1.0	10	0.8	16.7
MEAN	206.7			180.6			217.1			268.7				
DELTA I	PROJECTHDL	PREC	ISION											
	POOL 36		%	POOL 81		%	POOL 88		%	MEAN	MEAN			
	VARIANCE	CV	TOTAL	VARIANCE	CV	TOTAL	VARIANCE	CV	TOTAL	CV	% TOTAL			
TOTAL	9.8	5.4	100	3.6	4.9	100	2.2	5.5	100	5.2	100			
LAB	8.8	5.1	90	3.2	4.6	89	2.0	5.2	89	4.9	89.3			
RUN	0.2	0.8	2	0.1	0.8	3	0.1	1.0	3	0.9	2.7			
REPS.	0.7	1.5	8	0.3	1.4	9	0.2	1.5	7	1.5	6.0			
MEAN	58.4			39.16			27.45							

Variance components shown above are total, among labs, among runs-within labs, and among replicates.

CHAPTER 10

Data Management

Chapter 10: DATA MANAGEMENT

Data Collection 1.

The data collected for the DELTA study will be recorded on paper forms at each of the participating field centers. The local study data coordinator will be responsible for the secure and confidential management of original paper forms. Data unique to site-specific ancillary studies will be kept at the local DELTA field center with data management and analysis performed by individual study principal investigators. A microcomputer based data management system for DELTA developed by the Collaborative Studies Coordinating Center (CSCC) will provide all of the capabilities required for research data management for the multi-center trial, including: data entry, data editing, data transfer, and database processing.

Data Entry 2.

Data forms will be keyed using a full-screen FoxPro data entry system developed specifically for the DELTA study. The electronic screens will closely resemble the paper forms in format to facilitate online management and review of the data. Each data value will be edited during entry. The data entry system will flag each data value with a "status character" documenting the current editing status of the value (empty, skipped, passed edit, questionable, confirmed, etc.). Users will have the ability to flag, or annotate questionable data items. Updated data values will be entered and edited in the same manner as the original data values. Written data queries will be generated on a periodic basis for resolution by the local data or laboratory coordinator. Once the local center, or laboratory has responded in writing on the query, the necessary action to resolve the query will be recommended (the centers will make the changes) by the Coordinating Center.

Data Transfer 3.

Data files for the DELTA study will be generated by the microcomputer based data management system onto diskette. Copies of the electronic data files will be transferred by diskette to the following address:

Collaborative Studies Coordinating Center Attention: DELTA Central Receiving [name]

Each data transfer diskette should be sent in a protective diskette mailer. The original paper forms will be kept at the field center site by the study data coordinator. Field Centers will not send paper forms to the Coordinating Center unless specifically requested. The

frequency of data transfer by the field centers to the Coordinating Center will be every other week. Central agencies and laboratories (i.e., Food Analysis and Hemostasis laboratories) also send data on diskettes to the CSCC, and all information transferred electronically must be in a format that conforms to DELTA data transfer standards to insure complete and accurate processing.

4. Database Processing

The receipt of each data transfer diskette will be acknowledged by the CSCC, after being logged into the study inventory system. Any discrepancy discovered while processing the data will be communicated to the originating data coordinator or central agency in writing. The study data will be stored in a single collaborative database. All the data dictionary / schema definition facilities available by the data base management system will be used to document and format the database. Standard transaction validity checks will be applied to all updates to the database (e.g., to prevent the addition of records with duplicate keys, etc.). A journal file of all updates to the database will be maintained. Database backups will be made daily with the archival of the data files occurring monthly.

All data (paper and electronic) will be stored, processed, and analyzed within the CSCC office suite. At the CSCC, all access to office space containing data is controlled through manned reception areas. Visitors are screened by the receptionists and cannot move about without a CSCC escort. All office space is locked after working hours. Access to computer data files is controlled by passwords released only to those CSCC personnel who use the files. In addition, critical data files are encrypted.

A backup of the study database will be made daily to a separate file server on the CSCC local area network. Magnetic tape backups of the database will be made weekly, using a father/grandfather cycle with 5 generations. Once a month, the current backup tape will be removed from the cycle and permanently archived at the CSCC's off-site data storage facility. Output mailed to clinic staff will identify participants only by ID number. No individually identifiable information will distributed to clinical sites.

Data will be processed, and analyzed using in-house computers by CSCC staff.

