The Chairman of the Steering Committee, Project Officer, and other designated NHLBI staff will participate in these meetings in an ex-officio capacity, to facilitate communication between the Protocol Review Committee and Steering Committee.

The principal investigator of the Coordinating Center and designated Coordinating Center staff will attend these meetings (but will not have a vote) and will be responsible for preparing and presenting progress reports on the status of the study on an ongoing basis. These reports will include data on recruitment and randomization, as well as statistical tests and special analyses requested by the committee.

Members of the Protocol Review Committee are:

[name], Ph.D. (Chair) Department of Medicine Oregon Health Sciences University Portland, OR

[name]. Department of Food Science and Technology University of Georgia Athens, GA

[name], R.D. General Clinical Research Center University of Iowa Iowa City, IA

[name]. Pythagoras, Inc. Birmingham, AL

[name]. Division of Hematology University of Texas Medical School Houston, TX

E. Human Subjects Protection:

1. Informed Consent

Informed consent will be obtained from each participant before they are enrolled in the study. A draft Informed Consent form is found in the Appendix to this protocol. The Consent form will describe the risks and benefits of participating in the study, as well as the responsibilities of the participants and the investigators.

2. Privacy

Privacy in the context of this study includes confidentiality of data and personal information at the field center (see individual site descriptions below) and in handling and reporting of data by the Coordinating Center (see Chapter 9). It also includes discretion on the part of field center staff and arrangements for physical privacy during interviews and examinations.

3. Participant Screening and Feedback

Information obtained at screening, before enrollment, will be available at that time. Abnormal values found at screening will be reported to the participant and also, upon request, to his or her personal physician. Data will not be available until the very end of the study, because the protocol calls for batch analysis of all samples collected throughout.

4. Safety

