The DELTA study will evaluate the effects of various diets on blood lipids, and lipoproteins, clotting parameters and related variables. The diets will have varying composition but will not differ greatly from those consumed by many members of the public. All diets will be nutritionally adequate and meet subjects' calorie needs (they will be designed specifically to prevent weight change). The experimental diets will be planned using the RDA for women and men 25-50. The experimental treatments for the DELTA study are not expected to pose any risk. Since participants of this study are at increased risk of developing coronary heart disease, we will provide group instruction on the principles of a Step-1 diet at the end of each feeding periods. At the end of the study, all subjects will receive either individual or group instruction on the implementation of heart healthy dietary practices. Individuals for whom the diets are contraindicated because of preexisting conditions (for example, liver disease, kidney disease, clotting disorder) would not be eligible for participation according to defined exclusion criteria (see Chapter 6).

Information about food allergies will be collected during screening.

The collection of biological specimens and other information carries a small risk. For example, phlebotomy carries a risk of bruising and discomfort. This will be explained to the participant in the consent form.

Food safety procedures will be rigorously applied in order to protect participants against illness due to microbiological contamination of food. Application of specified food handling standards appropriate for their particular institution (hospital-based kitchen; other setting) will be employed. Individuals will be carefully instructed in the handling and storage of any take-home food or meals for example coolers and "blue ice" will be provided; Time-Temperature Indicator Labels (TTI's) (LifeLines Technology, Morris Plains, NJ) will be enclosed with instructions not to consume certain foods if the TTI indicates that holding temperatures have not been appropriate (See also Chapter 7). The consent form will include an explanation of the participants' obligation to handle take-out food according to instructions they will be given to maintain adequate sanitary conditions.

5. Safety Oversight

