Potential subjects will be screened for eligibility through a combination of telephone interviews and clinic visits as described in Chapter 6. Subjects who meet the eligibility requirements will be required to participate in a diet "run-in" period to take place during the two weeks immediately prior to randomization. The diet run-in period will serve to familiarize the subjects with the requirements of the study and to allow those subjects who feel that they can not tolerate the demands of the study to drop out prior to randomization. Since it is estimated that approximately 10% of the subjects will drop out during the run-in period, the number of prospective subjects entering this phase will be appropriately inflated. The length of the diet run-in period will be left up to the discretion of each individual Field Center but will not be less than three days nor longer than five days. The choice of diets and specific menus to be presented to the subjects during the diet run-in will likewise be left up to the discretion of the individual Field Centers. In all cases, however, the individual Field Centers will report to the Coordinating Center their specific protocol for the diet run-in period.

Information regarding subjects who have successfully completed the run-in period, have expressed continued interest in participating in the study, and have provided informed consent, will be forwarded to the Coordinating Center. The Coordinating Center will in turn provide a randomization schedule for each Field Center. Subject randomization will provide balanced assignments with respect to gender and race to each of the six dietary sequences. Balanced assignments will occur at the level of the Field Centers (as opposed to across the entire study population) to provide each Field Center with the greatest flexibility in implementing local Ancillary Studies.

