- a) A fasting venous blood will be drawn for insulin determination at EV1 for all participants. However, insulins, at the time of EV1, will be measured only on May Be Eligibles. For all others blood will be stored for analysis after EV2 if needed.
- b) Insulin Confirmation
 Insulin ≥ 70th% 3 μU/ml allows the May Be Eligibles from Step 2b EV1 to proceed to EV2
- C) Lipid & Insulin Criteria for Final Inclusion at EV2
 EV2 Fasting Cholestech is drawn

Average of Cholestech lipids from EV1 & EV2 must meet the following:

 Step 1
 Exclusion Average of EV1 & EV2

 TC
 < 25th% or > 90th% or

 LDL > 190 mg/dl

 TG
 < 30th% or > 500 mg/dl

 HDL > 70th%

Step 2 Inclusion Average of EV1 & EV2

HDL \leq 30th% or TG \geq 70th%

Individuals who are not excluded

(HDL > $30th\% \le 70th\%$ or TG $\ge 30th\% < 70th\%$) are May Be Eligibles and proceed to Step 3 for Insulin Confirmation

Step 3 Insulin for May Be Eligibles only

Average Insulin (EV1 & EV2) \geq 70th% for age, race and gender.

C. CHEMSCREEN EXCLUSIONS CRITERIA

Participants will have a fasting blood draw at EV2 in addition to the exclusions noted in Item 2 above. Participants can be excluded with abnormal values indicating metabolic disturbances or disease on a standard Chem screen. These include abnormal: CBC, hemoglobin, TSH or creatinine (> 1.3 mg/dl), glucose >130 mg/dl.

[figure not shown]
D. BLOOD PRESSURE HYPERTENSION

BP will be measured in standardized fashion at EV1 and EV2. The average of 2 BP readings at each visit will be used to determine the BP level at each visit. Individuals will be excluded in the average of their BP at EV1 and EV2 is

Systolic BP > 140 mmHg or Diastolic DBP > 90 mmHg

If the DBP \geq 100 mmHg or SBP \geq 160 mmHg at either Eligibility Visit 1 or Eligibility Visit 2, the applicant will be excluded. He/she will be informed of their blood pressure level and referred to their private physician or medical source.

DELTA/Protocol 2 Flow chart/BL/4-28-94

E. MEDICAL OR DIETARY EXCLUSIONS

- 1) Medical History
- Clinical evidence of cardiovascular disease including past myocardial infarction, angina, coronary occlusion, history of coronary artery bypass and/or congestive heart failure, stroke or peripheral vascular disease
- Diabetes mellitus (use of insulin, oral hypoglycemic agents or a fasting blood sugar > 130 mg/dl)
- Hypertension (use of anti-hypertensive medication or systolic pressure > 140 mmHG or diastolic pressure > 90 mmHG average on Eligibility Visits 1 and 2)

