Eligibility Visit 1-- The first eligibility visit will involve continued screening. A selfadministered questionnaire will include medical history, medication use, alcohol use, physical activity habits and exclusion criteria. A complete explanation of the study and the participants' expected level of commitment will be presented by clinic staff. Questions will be solicited and addressed. Measurement of blood pressure, height/weight, and a fasted lipid profile and venepuncture for insulin will be completed. Based on the information compiled at the first eligibility visit, exclusion will be completed or a second eligibility visit will be scheduled. Potential participants will be given directions to report to the second eligibility visit in a fasted state.

Should the blood chemistry results produce an exclusion value, the person will be called to discontinue further study eligibility screening.

Eligibility Visit 2--The second eligibility visit will begin with a review of the study explanation. Additional questions will be addressed. Blood pressure will be measured and a fasted lipid profile, insulin, and blood chemistries will be drawn. The diet run-in will be explained and the participant will be scheduled. Should the blood chemistry results produce an exclusion value, the person will be called to discontinue further study eligibility screening. A Participant Agreement will be used to clarify study expectations and to allow the participant to review them with family members or significant others before making a commitment to participate.

Diet Run-In includes a 3 - 5 day run-in period where the participant eats meals on site and follows other protocol requirements. A diet run-in phase will allow the prospective participant to experience the routine of a feeding study. The atmosphere, food palatability and intake limitations will be assessed by each participant. Weigh-ins will help with the assessment of caloric levels required for maintenance of body weight. Successful completion of the diet run-in is required. Participants who complete the run-in and remain interested must provide informed consent and sign the Participant Agreement to be randomized.

.

H. PROCEDURES TO BE COMPLETED AT EACH SCREENING-ELIGIBILITY VISIT INCLUDE:

Telephone Screening

Interview to obtain:

- 1. Sociodemographics
- 2. Medical History
- 3. Alcohol
- 4. Self-reported Weight
- 5. Special Diet
- 6. Study Requirements
- 7. Schedule EV1 for eligible candidates

EV1 Procedures

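### The only informed-consent step in the visit sequence comes after the screening blood draws and the feeding run-in

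*Protocol*

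**What the plan says.** **Where consent is placed.** Chapter 6, section G (Implementation), in the paragraph on the diet run-in: "Participants who complete the run-in and remain interested must provide informed consent and sign the Participant Agreement to be randomized". Chapter 5, section A describes what goes to the Coordinating Center so that it can randomize: "Information regarding subjects who have successfully completed the run-in period, have expressed continued interest in participating in the study, and have provided informed consent". The general statement in Chapter 2, section E.1 is "Informed consent will be obtained from each participant before they are enrolled in the study". Section E.3 of the same chapter puts screening ahead of that point: "Information obtained at screening, before enrollment, will be available at that time".

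**What comes earlier.** For Eligibility Visit 1 (EV1), section B of Chapter 6 says "A fasting venous blood will be drawn for insulin determination at EV1 for all participants", and section G says "Measurement of blood pressure, height/weight, and a fasted lipid profile and venepuncture for insulin will be completed". For Eligibility Visit 2 (EV2), section G says "Blood pressure will be measured and a fasted lipid profile, insulin, and blood chemistries will be drawn". Section B adds that EV1 blood from people who are not in the May Be Eligible group is kept for possible insulin assay after EV2. Section H lists 3 to 5 consecutive days of a 37% fat diet as the run-in.

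**What the consent form is for.** Chapter 2, section E.4: "phlebotomy carries a risk of bruising and discomfort. This will be explained to the participant in the consent form".

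**The concern.** A site that follows the visit sequence as written would ask people to fast, take their blood at two visits, store some of it and feed them a controlled diet, and would reach the consent form only with those who completed all of this and still wished to continue. The form that is meant to explain the risk of phlebotomy would then arrive after the screening phlebotomies.

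People who fail a screening criterion or leave in the run-in would not reach the consent step shown. Recruitment draws partly on employees and students of the participating institutions (Chapter 6, section I), for whom documented voluntary agreement before any procedure is of particular value.

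**Working it through.** No formula applies. The check is to follow consent, the Participant Agreement, blood sampling and feeding through the protocol in the order it gives.

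| Step | Procedures (Chapter 6, B, G and H) | Consent item listed? |
|---|---|---|
| Telephone screening | Interview; instruction to attend EV1 fasted | No |
| EV1 | Finger stick; venepuncture for insulin; storage of some samples | No. Study information and the Participant Agreement appear under the clinic interview |
| EV2 | Second finger stick; venepuncture for lipids, insulin, glucose, TSH and chemistry screen | No. Study information only |
| Run-in | Study diet for 3 to 5 days, weighing, compliance check | No |
| After run-in | Informed consent and signed Participant Agreement | **Yes** |
| Randomization | Diet sequence assigned | Not applicable |

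**Count before the consent step.** EV1 and EV2 each have one finger stick and one venepuncture, so a person who completes both has 1 + 1 = 2 of each, followed by 3 to 5 days of feeding if they enter the run-in. Someone excluded on the EV1 finger stick may have less: section B applies the EV1 venous draw to all participants, while section H limits it to those who still qualify.

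**Does the general promise cover screening?** Section E.1 of Chapter 2 ties consent to enrollment, and section E.3 describes screening as preceding enrollment. Consent taken after the run-in therefore satisfies E.1, and E.1 does not protect the screening stage.

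**Does the Participant Agreement fill the gap?** Appendix A lists the Consent Form (item 5) and the Participant Agreement (item 6) separately, and section G requires both after the run-in. The Agreement is described as setting out expectations and willingness to comply. Its timing also varies:
- section H lists it in the EV1 interview;
- section G has it reviewed at EV2 and signed after the run-in;
- Chapter 7, section A describes signing before it turns to the run-in.

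**Is a screening consent listed anywhere?** Appendix A has one Consent Form and no separate screening consent. The inclusion criteria in Chapter 6, section A require informed consent without saying when.

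**Does this reach the analysis?** Endpoints are drawn in weeks 5, 6 and 7 of each diet period. The working model in Chapter 4, section E has diet and period means, subject and subject-by-period effects and residual error; the covariates added for the power calculation in section G are gender, race, center and age. No screening lipid or insulin value enters either.

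**The case against.** The strongest reply is that the material which could settle the matter is not available. The consent form in Appendix B was removed from the text, the visit flow charts are not shown, and the two screening questionnaires are known only by title. Any of them could contain a screening consent. No sentence says that consent is first sought after the run-in: the Chapter 5 wording can be read as a list of conditions rather than a sequence, and the Chapter 6 wording states what randomization requires. This stands as a limit on certainty. It does not remove the point, because the intact text places consent once, after the run-in, and lists no earlier one.

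People are also not uninformed when blood is drawn. The EV1 narrative has a full explanation of the study, with questions answered, before it mentions any measurement, and the EV1 list puts study information and the Agreement ahead of the venepuncture, though after the finger stick. Each center's IRB reviews safety. This softens the concern, but explanation and a commitment form are not documented informed consent.

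Finally, most of the blood sampling (about 41 ml three times per diet period, plus the postprandial draws) follows randomization and so follows consent. That is correct. What remains is the two screening draws, the stored EV1 blood and the run-in.

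**Conclusion.** The point holds as a fault in the stated order of procedures: the one consent step the protocol places comes after two rounds of screening blood and the feeding run-in, and the general promise in Chapter 2 does not reach back to cover them. It is a matter of participant protection, with no effect on power or on the diet comparison.

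Three stronger readings are tempting, and the documents do not support them.

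- **That screened-out people and run-in dropouts certainly never consent.** This is an inference while the consent form and flow charts are unseen.
- **That about 11 people would be fed without consent.** The arithmetic is 100 / 0.90 = 111 entrants, less 100 = 11. It treats 100 as the number randomized, whereas Chapter 4, section F assumes 100 who complete the study. Table 2 does allocate 100 sequences, but without allowance for later dropout. The documents support only a description: everyone excluded at EV1 or EV2, and roughly 10% of run-in entrants.
- **That the trial data could be challenged.** Nothing in the documents says so, and although screening values decide eligibility, they do not enter the diet comparison.

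The conclusion assumes that sites follow the sequence and lists in Chapter 6 as written, and that no screening consent sits in the material not shown. If one does, what remains is to state it in the visit lists.

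**What to change.** Make signed informed consent, or a dedicated screening consent, the first item of EV1, before the finger stick. It should cover the screening blood at both visits, storage of the EV1 sample and the run-in. Keep the step after the run-in as a reaffirmation of consent to the feeding trial before randomization.

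Then bring these places into line: Chapter 2, section E.1 (consent before any study procedure); Chapter 5, section A; Chapter 6, sections G and H; and Chapter 7, section A, giving a single time for signing the Participant Agreement. If a separate screening consent is chosen, add it to the forms list in Appendix A.

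The cost is one extra signature and some staff time spent on people who later screen out. Sample size and analysis are unchanged.
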